5.2 Treatment Delays and Schedule Modification

Brief interruptions and delays in the 21-day cycle may occasionally be required due to travel delays, airport closure, inclement weather, family responsibilities, security alerts, government holidays, etc. This can also extend to complications of disease or unrelated medical illness not related to disease progression. These delays will not be considered protocol violations.

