4. TREATMENT PLAN

4.1 Suberoylanilide Hydroxamic Acid (VORINOSTAT) Administration

Treatment will be administered on an outpatient basis. Reported adverse events and potential risks are described in Section 6. Appropriate dose modifications for VORINOSTAT are described in Section 5. No investigational or commercial agents or therapies other than those described below may be administered with the intent to treat the patient's malignancy.

A cycle of therapy will consist of VORINOSTAT 200mg twice daily administered orally for 14 days followed by a seven day break on a 21 day cycle for the first cycle. If tolerated, the dose may be increased after the 2nd cycle to 200 mg TID x 14/21 days. If necessary, dose de-escalation may be instituted by reducing one of the daily doses by 100 mg; so, for example, patients might receive an am dose of 300 mg and a pm dose of 200 mg. Rituximab will be infused on day 1 of each cycle at the standard dose of 375 mg/m². Radiological assessment by CT and/or PET scan will take place at baseline and after every three cycles (every 3 months). Response will be assessed by standard criteria (Cheson BD, *et al* 1999). Toxicity will be assessed on days 1 and 8 of every cycle, and graded using the NCI CTCAE version 3.0. Patients with measurable response or stable disease may continue receiving VORINOSTAT until progression. Patients who achieve CR will receive two further cycles of VORINOSTAT plus rituximab and then discontinue drug. Patients who achieve complete response may be restarted on drug in the event of relapse six months or greater from the time of initial CR, given the chronic relapsing nature of indolent lymphomas. Compliance with treatment will be monitored by use of drug diaries.

Because many drugs including antineoplastic agents are metabolized by the cytochrome P450 system, there is a potential for interaction of VORINOSTAT with concomitantly administered drugs. The case report form must capture the concurrent use of all other drugs, over-the-counter medications, or alternative therapies.

Patient compliance will be monitored using drug diaries, which will be reviewed on day 1 of each cycle after cycle 1.

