5. DOSING DELAYS/DOSE MODIFICATIONS

5.1 Vorinostat Dose Reductions for Toxicity:

Treatment will be administered at 100 mg daily less than their previous dose for patients who present to treatment and are found to have $ANC \geq 500$, but ≤ 1000 , or platelet counts $\geq 50K$ but $\leq 75K$. This dose reduction is reversible with normalization of counts.

Treatment will be held for patients who present with:

1. non-hematologic toxicity of grade 3 or 4, until toxicity resolves to below grade 2. These patients will restart at 100 mg daily less than their previous dose. If this dose leads to recurrence of the toxicity at grade 3 or greater, the patient will come off study.
2. hematologic toxicity of ANC <500, or platelet count <50K. Should dose need to be held for greater than two weeks, upon recovery of ANC >1000 or platelet count >50 patient may restart at 100 mg daily less than their previous dose. If this dose also leads to ANC<500 or platelet count <50, then patient should come off study.

Treatment will be discontinued in patients who experience toxicity of grade 3 or greater that does not resolve within 3 weeks. Requirement for more than two dose reductions mandates removal from the study. Delay of protocol treatment for more than four weeks from date of scheduled treatment mandates removal from protocol treatment, unless there are extenuating circumstances and approved by the principal investigator.

Lovenox Dose Reductions for Toxicity:

Hematologic Toxicity: If platelet count drops to <50K, lovenox should be held until platelets recover.

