7. STUDY CALENDAR

Baseline evaluations are to be conducted within 1 week prior to administration of protocol therapy. Scans and x-rays must be done within 4 weeks prior to the start of therapy. For subsequent weeks, the studies may be performed within \pm 2 days of the indicated dates.

	Pre-Study	Wk 1	Wk 2	Wk 3	Wk 4	Wk 5	Wk 6	Wk 7	Wk 8	Wk 9	Wk 10	Wk 11	Wk 12+ ^g	Off Study
VORINOSTAT ^{a, g}		X	X		X	X		X	X		X	X		
Rituximab		X			X			X			X			
Lovenox		X	X	X	X	X	X	X	X	X	X	X	X	
Informed consent	X													
Demographics	X													
Medical history	X													
Height	X													
B-HCG ^b	X													
Record concurrent medications	X	X-----X												
Physical exam	X	X			X			X			X			X
Vital signs	X	X			X			X			X			X
Weight	X	X			X			X			X			X
Performance status	X	X			X			X			X			X
CBC w/diff, plts	X	X			X			X			X			X
Serum chemistry ^c	X	X			X			X			X			X
Correlatives ⁱ	X		X											
Adverse event evaluation		X-----X												X
Tumor measurements	X	Tumor measurements are repeated every 3 cycles (~9 weeks) ^j . Bone marrow assessment should be done within 4 weeks of starting therapy, and repeated every 3 cycles if the initial marrow shows involvement by lymphoma. Documentation (radiologic) must be provided for patients removed from study for progressive disease.												X ^d
Radiologic evaluation	X	CT scans are repeated every 3 cycles (~9 weeks) ^j . Follow up PET scans for patients with PET positive disease is optional, but suggested.												X ^d
Bone marrow	X ^h									X				

- a: VORINOSTAT: Starting dose 200mg orally twice daily for 2 weeks, followed by 1 week of rest (21 day cycle).
- b: Serum pregnancy test (women of childbearing potential).
- c: Albumin, alkaline phosphatase, total bilirubin, bicarbonate, BUN, calcium, chloride, creatinine, glucose, LDH, phosphorus, potassium, total protein, SGOT [AST], SGPT [ALT], sodium.
- d: Off-study evaluation.
- g. Patients with partial response or stable disease may continue to receive VORINOSTAT until progression. Patients who achieve CR will receive two further cycles of VORINOSTAT and then discontinue drug. Follow up radiological studies will continue every three months for one year, then every six months for the next two years.
- h. Bone Marrow aspiration and biopsy may be performed up to four weeks prior to starting study drug, and if positive should be repeated every three cycles.
- i. For details see section 11.

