10. STATISTICAL CONSIDERATIONS

10.1 Study Design/Endpoints

Response rate (CR+PR) will be the primary endpoint. An underlying 20% response rate will be regarded as not sufficiently active, and the trial is designed to have little chance of missing a 40% response rate. A two-stage design will be used. In the first stage, 17 patients will be enrolled. If 4 or more respond, accrual will continue to a total of 33 patients, with 10 or more responses regarded as evidence of sufficient activity to warrant further investigation. If the true response rate is 20%, the proposed design has a 90% chance of declaring vorinostat plus rituximab insufficiently active, and a 55% chance of stopping early. If the true response rate is 40%, there is a 89% chance of concluding VORINOSTAT is sufficiently active. All patients beginning VORINOSTAT therapy will be included in response rates calculations, which will include exact binomial confidence intervals.

All reportable adverse events will be monitored by the PI and CRA, and reported as described in section 10. Reportable and non-reportable adverse events are routinely tabulated for phase II consortium trials as the reports arrive. The time to progression and overall survival will be estimated using the product-limit method of Kaplan and Meier. Toxicity information recorded will include the type, severity, time of onset, time of resolution, and the probable association with the study regimen. Tables will be constructed to summarize the observed incidence by severity and type of toxicity. Baseline information (e.g. the extent of prior therapy, extent of disease) and demographic information will be presented, as well, to describe the patients treated in this Phase II study.

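### On-treatment scans follow cycle count and no rule holds the scan date when a cycle is delayed, so time to progression is dated somewhat later in patients with more interruptions.

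*Combined protocol and SAP*

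**What the plan says.** Three places set on-treatment imaging by cycle count. Section 4.1 says that it "will take place at baseline and after every three cycles", and adds in brackets that this means three-monthly. The Section 7 calendar says that "CT scans are repeated every 3 cycles (~9 weeks", and Section 8 repeats the nine-week figure. The calendar allows two days either side of the indicated dates. It does not say whether those dates move when a cycle is delayed.

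Two sections allow cycles to slip.
- **Section 5.1:** treatment is held for specified toxicities, and "Delay of protocol treatment for more than four weeks from date of scheduled treatment mandates removal from protocol treatment", unless the principal investigator approves an exception.
- **Section 5.2:** "Brief interruptions and delays in the 21-day cycle may occasionally be required due to travel delays", among other causes that include complications of disease. No number of days is given, and such delays are not violations.

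Section 9.2 exempts exactly these delays from its ban on deviations.

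Two scan rules stand apart. After CR, imaging runs on calendar time. After one year with two consecutive PRs, the interval may become four cycles.

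Objective 1.1 names time to progression. Section 10.1 gives its whole analysis: "The time to progression and overall survival will be estimated using the product-limit method of Kaplan and Meier". It has no rule for dating progression and none for late or unequally spaced scans.

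**The concern.** Progression in Section 8.1 is defined on lesions, and the calendar requires radiologic documentation for removal for progressive disease. The recorded date is therefore usually the date of a scan. If the scan waits for the third cycle to finish, each week of delay moves it back a week.

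The delays are not random. Under 5.1 they follow toxicity, and under 5.2 they may follow complications of the disease. Scan spacing then depends on how the patient is faring, and poorer tolerance lengthens the measured time to progression. The Kaplan-Meier estimate takes the detection dates at face value. At stake is the accuracy of one descriptive estimate, and whether patients within the trial are measured on the same footing.

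**Working it through.** **The plan's own figures.** Section 10.1 states that "Response rate (CR+PR) will be the primary endpoint", that "An underlying 20% response rate will be regarded as not sufficiently active", and that "the trial is designed to have little chance of missing a 40% response rate". The rule is to continue with at least 4 responders of 17, and to declare activity with at least 10 of 33. Exact binomial calculation:
- Early stop at 20%: P(X ≤ 3 | n = 17) = 0.5489 (plan: 55%).
- Declared inactive at 20%: 1 − Σ over x ≥ 4 of P(X₁ = x)·P(X₂ ≥ 10 − x | n = 16) = 1 − 0.0989 = 0.9011 (plan: 90%).
- Declared active at 40%: 0.8884 (plan: 89%).

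All three reproduce. They depend on counts of responders and not on scan dates.

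**Scan spacing.** A cycle is 21 days, so spacing = 3 × (3 weeks + delay per cycle):
- no delay: 9 weeks
- one 1-week delay in three cycles: 9 + 1 = 10 weeks
- 1 week in every cycle: 3 × 4 = 12 weeks
- 4 weeks in every cycle (the 5.1 limit without an exception): 3 × 7 = 21 weeks

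**Detection lag.** The documents give no expected median and no delay frequency. I assume exponential time to progression with a median of 26, 52 or 104 weeks, and date progression at the first scan at or after it occurs. With λ = ln 2 / median and scans every L weeks, mean lag = L / (1 − e^(−λL)) − 1/λ.

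Example, median 26 weeks: λ = 0.02666 and 1/λ = 37.51. At L = 9 the lag is 9/0.2133 − 37.51 = 4.68 weeks. At L = 12 it is 12/0.2738 − 37.51 = 6.32 weeks. The excess is 1.64 weeks.

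| Spacing | Lag, median 26 | Lag, median 52 | Lag, median 104 | Excess over 9 weeks |
|---|---|---|---|---|
| 9 weeks | 4.68 | 4.59 | 4.54 | – |
| 10 weeks | 5.22 | 5.11 | 5.06 | about 0.5 |
| 12 weeks | 6.32 | 6.16 | 6.08 | 1.5–1.6 |
| 21 weeks | 11.47 | 10.99 | 10.74 | 6.2–6.8 |

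For irregular delays I used simulation (200,000 patients per scenario). If each cycle has a 20% chance of a delay uniform on 0 to 4 weeks, the excess is about 0.8 week at all three medians.

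**The two stated intervals.** Three months is about 13 weeks. With L = 13 and no delay, the lag is 13/0.2929 − 37.51 = 6.87 weeks at a median of 26, and 13/0.0830 − 150.04 = 6.59 weeks at a median of 104 (unrounded denominators 0.29289 and 0.082996). That is 2.0–2.2 weeks more than at 9 weeks. The unresolved wording alone matters more than occasional delays do.

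**The case against.** Several points on the other side stand.

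- **Size of the delays.** The four-week figure is in 5.1 only; 5.2 speaks of brief and occasional interruptions. A reader might infer that both sections allow four weeks in cycle after cycle. The documents do not support that. Section 5.1 also stops treatment for grade 3 or greater toxicity unresolved at three weeks, takes patients off study for specified recurrent toxicity after a reduction, and removes those who need more than two dose reductions. The 21-week spacing is a ceiling.
- **Lag without delays.** About 4.5 weeks of lag exists at perfect nine-week spacing and would remain after any rescheduling.
- **Other routes to detection.** Patients are examined each cycle, off-study imaging is required, and a need for localized radiotherapy counts as progression (4.3.5). Some progressions will be found between scheduled scans, so the model overstates the lag. Post-CR imaging is already on calendar time.
- **Low consequence.** Time to progression has no test, threshold or comparator, and there are at most 33 patients.

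It could also be said that the nine-week gloss and the two-day window already fix scans to the calendar. That reading is possible but not secure: the gloss is true only of undelayed cycles, the window does not say whether its dates move, and 4.1 gives a different gloss.

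A reader might also infer that delays shift the observed median by a whole scan interval. With a true median of 26 weeks, the observed median is 27 weeks if everyone is scanned every 9 weeks and 36 if half are scanned every 12. This is an artefact of the scan grid: in the mixed group 49.3% are detected by week 27, so the median jumps to the next step. Over true medians from 26 to 104 weeks in half-week steps (157 values), the shift is zero in 98, negative in 14 and nine weeks in only 11, with an average of about 1.2 weeks. For the same mixture at a median of 26, the mean lag rises by half of 1.64, about 0.8 week.

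**Conclusion.** The gap is real and its direction is clear. On-treatment scans move with delayed cycles, delays are permitted and partly driven by toxicity or disease, and no rule holds the scan date. Scan-detected progression is then dated later in patients with more interruptions.

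The likely size is small: about 0.5–0.8 week of extra mean lag for occasional delays, 1.5–1.6 weeks if every cycle slips by a week, and 6.2–6.8 weeks at a ceiling that other 5.1 rules make unlikely. These figures rest on an assumed exponential distribution, assumed medians of 26 to 104 weeks, assumed delay patterns, and detection only at scheduled scans.

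A reader might go on to infer that the trial's main conclusion is at risk. It is not: the primary endpoint is response rate, its two-stage properties reproduce, and time to progression is descriptive. This is a cheap improvement to consider and not a flaw that undermines the design.

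**What to change.** - **Anchor the scans.** In Section 4.1, the Section 7 calendar and Section 8, count on-treatment scans in weeks from Cycle 1 Day 1 with a fixed window (for example ±1 week), whether or not treatment is delayed. Leave the separate rules after CR and after two consecutive PRs as they are.
- **State one interval.** Reconcile the roughly nine weeks of Sections 7 and 8 with the three months of Section 4.1.
- **Optional.** In 10.1, add an interval-censored (Turnbull) estimate of time to progression, running from the last scan without progression to the first with it, as a sensitivity analysis.

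The cost is wording in three sections and, if wanted, one extra analysis. No treatment rule changes. The downside is that some scans will fall inside a delayed cycle, and patients with delays will be scanned more often than under the cycle-count rule, though not more often than the stated interval.

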6. PHARMACEUTICAL INFORMATION

6.1 Suberoylanilide Hydroxamic Acid (NSC 701852)

Chemical Name: N-hydroxy-N'-phenyl-octane-1,8-dioic acid diamide;
N-hydroxyl-N'-phenyl (9CI) octanediamide

Other Names: VORINOSTAT, L-001079038, WIN 64652, MSK390, AP390

Classification: Antineoplastic

CAS Registry Number: 149647-78-9

Molecular Formula: C₁₄H₂₀N₂O₃ **M.W.:** 264

Approximate Solubility: Water ≤ 5 mg/mL

Description: Histone deacetylase (HDAC) inhibitor

Mode of Action: Histone deacetylases (HDACs) are a family of enzymes that regulate chromatin remodeling and gene transcription via the dynamic process of acetylation and deacetylation of core histones.

Suberoylanilide hydroxamic acid, a potent inhibitor of HDAC activity, binds directly to the catalytic pocket of HDAC enzymes. VORINOSTAT causes G1 or G2 phase cell-cycle arrest, apoptosis, or differentiation in cultured transformed cells.

How Supplied: Suberoylanilide hydroxamic acid is supplied by Merck and Co., Inc. Suberoylanilide hydroxamic acid is supplied in the following strengths:

1. a white, opaque gelatin capsule containing 100 mg (size 3 capsule) of suberoylanilide hydroxamic acid
2. a white, opaque gelatin capsule containing 200 mg (size 1 capsule) of suberoylanilide hydroxamic acid.

The inactive ingredients contained in each capsule are microcrystalline cellulose, sodium croscarmellose, and magnesium stearate.

Suberoylanilide hydroxamic acid 100 mg capsules are supplied in bottles of 120 capsules and 200 mg capsules are supplied in bottles of 100 capsules.

Storage: Store suberoylanilide hydroxamic acid capsules at room temperature, 15 to 30 °C (59 to 86 °F). Transient temperature spikes up to 40 °C (104 °F) for up to 24 hours are permissible.

Stability: Shelf life stability studies of the intact bottles are ongoing.

Route of Administration: Orally

Method of Administration: Unless otherwise stated in the protocol, suberoylanilide hydroxamic acid capsules must be administered whole. The absolute bioavailability of suberoylanilide hydroxamic acid under fasted or fed conditions is approximately 46%. Oral administration with food does not appear to substantially alter the rate or extent of absorption.

Potential Drug Interactions: In cultured human hepatocytes, suberoylanilide hydroxamic acid was shown to inhibit CYP2B6, CYP2C9, CYP2C19, and CYP3A4 isoenzymes. Therefore, it is possible that suberoylanilide hydroxamic acid may interact with drugs that are metabolized by the P450 CYP isoenzymes. Caution should be exercised when combining the study agent with medications that are metabolized by these isoenzymes.

Special Handling: VORINOSTAT is an anticancer drug. Powder spills from VORINOSTAT capsules due to damaged or broken capsules should be cleaned up carefully so as to minimize inhalation. The affected area must be washed at least 3 times with ethyl alcohol, followed by water.

Patient Care Implications: Because VORINOSTAT's dose limiting toxicities are anorexia, dehydration, diarrhea, and fatigue, patients should maintain adequate fluid and food intake. Encourage patients to seek a nutritional consult.

Comprehensive Adverse Events and Potential Risks List (CAEPR):

The Comprehensive Adverse Event and Potential Risks list (CAEPR) provides a single list of reported and/or potential adverse events (AE) associated with an agent using a uniform presentation of events by body system. In addition to the comprehensive list, a subset, the Agent Specific Adverse Event List (ASAEL), appears in a separate column and is identified with **bold** and *italicized* text. This subset of AEs (ASAEL) contains events that are considered 'expected' for expedited reporting purposes only. Refer to the 'CTEP, NCI Guidelines: Adverse Event Reporting Requirements' <http://ctep.cancer.gov/reporting/adeers.html> for further clarification. *Frequency is provided based on 299 patients.* Below

is the CAEPR for VORINOSTAT (vorinostat).

Version 2.3, November 30, 2006¹

Adverse Events with Possible Relationship to VORINOSTAT (Vorinostat) (CTCAE v3.0 Term) [n=299 patients]			'Agent Specific Adverse Event List' (ASAEL)
Likely (>20%)	Less Likely (<=20%)	Rare but Serious (<3%)	
BLOOD/BONE MARROW			
Hemoglobin			Hemoglobin
Leukocytes (total WBC)			Leukocytes
	Lymphopenia		Lymphopenia
Neutrophils/granulocytes (ANC/AGC)			Neutrophils/granulocytes (ANC/AGC)
Platelets			Platelets
CARDIAC ARRHYTHMIA			
	Prolonged QTc interval		
COAGULATION			
	INR (International Normalized Ratio of prothrombin time)		
CONSTITUTIONAL SYMPTOMS			
Fatigue (asthenia, lethargy, malaise)			Fatigue (asthenia, lethargy, malaise)
	Fever (in the absence of neutropenia, where neutropenia is defined as ANC <1.0 x 10 ⁹ /L)		
	Rigors/chills		
Weight loss			Weight loss
DERMATOLOGY/SKIN			
	Hair loss/alopecia (scalp or body)		
		Dermatology/Skin – Other: skin necrosis	
GASTROINTESTINAL			
Anorexia			Anorexia
	Constipation		
	Dehydration		Dehydration
Diarrhea			Diarrhea
	Dry mouth/salivary gland (xerostomia)		
	Heartburn/dyspepsia		
Nausea			Nausea
	Taste alteration (dysgeusia)		
Vomiting			Vomiting
INFECTION			

	Febrile neutropenia (fever of unknown origin without clinically or microbiologically documented infection)(ANC <1.0 x 10e9/L, fever >=38.5 degrees C)		
	Infection with normal ANC or Grade 1 or 2 neutrophils - Select		
	Infection (documented clinically or microbiologically) with Grade 3 or 4 neutrophils (ANC <1.0 x 10e9/L - Select		
LYMPHATICS			
	Edema: limb		
METABOLIC/LABORATORY			
	Albumin, serum-low (hypoalbuminemia)		
	Alkaline phosphatase		
	ALT, SGPT (serum glutamic pyruvic transaminase)		
	AST, SGOT (serum glutamic oxaloacetic transaminase)		
	Bilirubin (hyperbilirubinemia)		
	Calcium, serum-low (hypocalcemia)		
	Creatinine		
	Glucose, serum-high (hyperglycemia)		Glucose, serum-high(hyperglycemia)
	Magnesium, serum-high (hypermagnesemia)		
	Phosphate, serum-low (hypophosphatemia)		
	Potassium, serum-low (hypokalemia)		
	Sodium, serum-low (hyponatremia)		
MUSCULOSKELETAL/SOFT TISSUE			
	Musculoskeletal/Soft Tissue - Other (muscle spasms)		
	Muscle weakness, generalized or specific area (not due to neuropathy) - Select		
NEUROLOGY			
	Dizziness		
	Neuropathy: sensory		

PAIN			
	Pain - abdomen NOS		
	Pain - head/headache		
PULMONARY/UPPER RESPIRATORY			
	Cough		
	Dyspnea (shortness of breath)		
VASCULAR			
	Thrombosis/thrombus/embolism		

¹This table will be updated as the toxicity profile of the agent is revised. Updates will be distributed to all Principal Investigators at the time of revision. The current version can be obtained by contacting [contact]. Your name, the name of the investigator, the protocol and the agent should be included in the e-mail.

Also reported on VORINOSTAT (vorinostat) trials but with the relationship to VORINOSTAT (vorinostat) still undetermined:

ALLERGY/IMMUNOLOGY - vasculitis

CARDIAC ARRHYTHMIA - atrial fibrillation; palpitations; ventricular fibrillation

CARDIAC GENERAL - cardiac ischemia/infarction; hypertension; hypotension

COAGULATION - PTT

CONSTITUTIONAL SYMPTOMS - insomnia; sweating

DEATH – death NOS

DERMATOLOGY/SKIN –nail changes; pruritus; rash; ecchymosis

GASTROINTESTINAL - dysphagia; esophagitis; flatulence; gastritis; mucositis/stomatitis

HEMORRHAGE/BLEEDING - epistaxis; hematuria; hemoptysis; petechiae

INFECTION – infection – NOS

METABOLIC/LABORATORY – hypercalcemia; hyperkalemia; hypernatremia; hypoglycemia; hypomagnesemia; proteinuria

MUSCULOSKELETAL/SOFT TISSUE - gait/walking

NEUROLOGY - confusion

PAIN - back pain; chest/thorax pain; flank pain; gingival pain; joint pain; limb pain; muscle pain; pharyngolaryngeal pain

PULMONARY/UPPER RESPIRATORY - sinus congestion

RENAL/GENITOURINARY – urinary incontinence; urinary retention

VASCULAR - deep vein thrombosis

Note: VORINOSTAT (vorinostat) in combination with other agents could cause an exacerbation of any adverse event currently known to be caused by the other agent, or the combination may result in events never previously associated with either agent.

Availability

VORINOSTAT is an investigational agent supplied to investigators by Merck and Co. Inc.

